### 6.1.2 Sample size calculations for immunogenicity

The main goals of this trial regarding immunogenicity outcomes involve a preliminary estimation of response rates based on data from the BAMA, ICS, and nAb assays among vaccinees at 2 weeks following vaccination. No adjustment for multiple comparisons will be made for the use of multiple assays. The precision with which the true response rate can be estimated from the observed data depends on the true underlying response rate and the sample size. Two-sided 95%

confidence intervals for the response rate based on observing a particular rate of responses in the vaccinees is shown in [Table 6-3](#). Calculations are done using the score test method [36]. The n = 13, 22, 36 assumes a 10% rate of missing immunogenicity data.

**Table 6-3 Two-sided 95% confidence intervals for the true response rate based on observing a particular rate of responses in the vaccinees (n = 13, 22, 36)**

No. of responses	Observed response rate (%)	CI
n = 13		
3/13	23.1	[8.2, 50.2]
5/13	38.5	[17.7, 64.5]
7/13	53.8	[29.1, 76.8]
11/13	84.6	[57.8, 95.7]
12/13	92.3	[66.7, 98.6]
n = 22		
3/22	13.6	[4.8, 33.3]
5/22	22.7	[10.1, 43.4]
7/22	31.8	[16.4, 52.7]
11/22	50.0	[30.7, 69.3]
15/22	68.2	[47.3, 83.6]
19/22	86.4	[66.7, 95.3]
20/22	90.9	[72.2, 97.5]
n = 36		
3/36	8.3	[2.9, 21.8]
5/36	13.9	[6.1, 28.7]
7/36	19.4	[9.8, 35]
11/36	30.6	[18, 46.9]
15/36	41.7	[27.1, 57.8]
19/36	52.8	[37, 68]
23/36	63.9	[47.6, 77.5]
27/36	75	[58.9, 86.2]
33/36	91.7	[78.2, 97.1]

## 6.2 Randomization

The randomization sequence will be obtained by computer-generated random numbers and provided to each HVTN CRS through a Web-based randomization system. The randomization will be done in blocks to ensure balance across arms. At each institution, the pharmacist with primary responsibility for dispensing study products is charged with maintaining security of the treatment assignments (except in emergency situations as specified in the HVTN Manual of Operations (MOP)).

## 6.3 Blinding

Participants and site staff (except for site pharmacists) will be blinded as to participant treatment arm assignments (eg, vaccine or control). Study product assignments are accessible to those HVTN CRS pharmacists, DAIDS protocol pharmacists and contract monitors, and SDMC staff who are required to know

this information in order to ensure proper trial conduct. Any discussion of study product assignment between pharmacy staff and any other HVTN CRS staff is prohibited. The HVTN SMB members also are unblinded to treatment assignment in order to conduct review of trial safety.

When a participant leaves the trial prior to study completion, the participant will be told he or she must wait until all participants are unblinded to learn his or her treatment assignment.

Emergency unblinding decisions will be made by the site investigator. If time permits, the HVTN 122 PSRT should be consulted before emergency unblinding occurs. See the HVTN MOP for more information.

## **6.4 Statistical analyses**

This section describes the final study analyses, unblinded as to treatment arm assignment. All data from enrolled participants will be analyzed according to the initial randomization assignment regardless of how many vaccinations they received. In the rare instance that a participant receives the wrong treatment at a specific vaccination time, the Statistical Analysis Plan (SAP) will address how to analyze the participant's safety data. Analyses are modified intent-to-treat in that individuals who are randomized but not enrolled do not contribute data and hence are excluded. Because of blinding and the brief length of time between randomization and enrollment—typically no more than 4 working days—very few such individuals are expected.

Analyses for primary endpoints will be performed using SAS and R. All other descriptive and inferential statistical analyses will be performed using SAS, StatXact, or R statistical software.

No formal multiple comparison adjustments will be employed for multiple safety endpoints, multiple primary immunogenicity endpoints, or secondary endpoints. However, multiplicity adjustments will be made for certain immunogenicity assays, as discussed below, when the assay endpoint is viewed as a collection of hypotheses (eg, testing multiple peptide pools to determine a positive response).

### **6.4.1 Analysis variables**

The analysis variables consist of baseline participant characteristics, safety, and immunogenicity for primary- and secondary-objective analyses.

### **6.4.2 Baseline comparability**

Treatment arms will be compared for baseline participant characteristics using descriptive statistics.

### 6.4.3 Safety/tolerability analysis

Since enrollment is concurrent with receiving the first vaccination, all participants will have received at least 1 vaccination and therefore will provide some safety data.

#### 6.4.3.1 Reactogenicity

The number and percentage of participants experiencing each type of reactogenicity sign or symptom will be tabulated by severity and treatment arm and the percentages displayed graphically by arm. For a given sign or symptom, each participant's reactogenicity will be counted once under the maximum severity for all injection visits. In addition to the individual types of events, the maximum severity of local pain or tenderness, induration or erythema, and of systemic symptoms will be calculated. Kruskal-Wallis tests will be used to test for differences in severity between arms.

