## 5 Objectives and endpoints

### 5.1 Primary objectives and endpoints

*Primary objective 1:*

To evaluate the safety and tolerability of 1 injection of gp145 C.6980 at 2 dose levels with alum adjuvant in HIV-seronegative low risk adults

*Primary endpoints 1:*

Frequency of severe local and systemic reactogenicity signs and symptoms: pain, tenderness, maximum severity of pain and/or tenderness, erythema, induration, fever, malaise/fatigue, myalgia, headache, nausea, vomiting, chills, arthralgia, maximum severity of systemic symptoms (graded using the Division of AIDS Table for Grading the Severity of Adult and Pediatric Adverse Events. Corrected Version 2.1, dated July 2017)

Frequency of AEs by treatment arm, by body system, Medical Dictionary for Regulatory Activities (MedDRA) preferred term, severity, and assessed relationship to study products (graded using the Division of AIDS Table for Grading the Severity of Adult and Pediatric Adverse Events. Corrected Version 2.1, dated July 2017)

Serious adverse events (SAEs) throughout the active surveillance period

Laboratory measures of safety: white blood cells (WBC), neutrophils, lymphocytes, hemoglobin, platelets, ALT, and creatinine at baseline and following vaccinations, by treatment arm (graded using the Division of AIDS Table for Grading the Severity of Adult and Pediatric Adverse Events. Corrected Version 2.1, dated July 2017)

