### 5.2 Secondary objectives and endpoints

*Secondary objective 1:*

To evaluate the safety and tolerability of 3 injections of gp145 C.6980 at 2 dose levels with alum adjuvant in HIV-seronegative low risk adults

*Secondary endpoints 1:*

Frequency of severe local and systemic reactogenicity signs and symptoms: pain, tenderness, maximum severity of pain and/or tenderness, erythema, induration, fever, malaise/fatigue, myalgia, headache, nausea, vomiting, chills, arthralgia, maximum severity of systemic symptoms (graded using the Division of AIDS Table for Grading the Severity of Adult and Pediatric Adverse Events. Corrected Version 2.1, dated July 2017)

Frequency of AEs by treatment arm, by body system, Medical Dictionary for Regulatory Activities (MedDRA) preferred term, severity, and assessed relationship to study products (graded using the Division of AIDS Table for Grading the Severity of Adult and Pediatric Adverse Events. Corrected Version 2.1, dated July 2017)

SAEs throughout the active surveillance period

Laboratory measures of safety: white blood cells (WBC), neutrophils, lymphocytes, hemoglobin, platelets, ALT, and creatinine at baseline and following vaccinations, by treatment arm (graded using the Division of AIDS Table for Grading the Severity of Adult and Pediatric Adverse Events. Corrected Version 2.1, dated July 2017)

*Secondary objective 2:*

To characterize the immunogenicity of 1 injection of gp145 C.6980 at 2 dose levels with alum adjuvant in HIV-seronegative low risk adults

*Secondary endpoints 2:*

Response rates and levels of vaccine-induced binding antibodies to HIV proteins measured by the binding antibody multiplex assay (BAMA) at 2 weeks following the first vaccination

*Secondary objective 3*

To characterize the immunogenicity of 3 injections of gp145 C.6980 at 2 dose levels with alum adjuvant in HIV-seronegative low risk adults

*Secondary endpoints 3:*

Response rates and levels of vaccine-induced binding antibodies to HIV proteins measured by the BAMA at 2 weeks following the third vaccination

Response rates and levels of CD4+ and CD8+ T cells measured by intracellular cytokine staining (ICS) at 2 weeks following the third vaccination

Response rates and levels of neutralizing antibody responses against HIV-1 isolates at 2 weeks following the third vaccination

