#### 6.4.3.2 AEs and SAEs

AEs will be summarized using MedDRA System Organ Class and preferred terms. Tables will show by treatment arm the number and percentage of participants experiencing an AE within a System Organ Class or within preferred term category by severity or by relationship to study product. For the calculations in these tables, a participant with multiple AEs within a category will be counted once under the maximum severity or the strongest recorded causal relationship to study product. Formal statistical testing comparing arms is not planned since interpretation of differences must rely heavily upon clinical judgment.

A listing of SAEs reported to the DAIDS Regulatory Support Center (RSC) Safety Office will provide details of the events including severity, relationship to study product, time between onset and last vaccination, and number of vaccinations received.

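### Reactogenicity is planned only as the maximum over all injections, so the one-injection primary objective has no first-injection reactogenicity frequency by arm

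*Protocol*

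**What the plan says.** Protocol 5.1 (repeated in SAP 4.1) has one primary objective: "To evaluate the safety and tolerability of 1 injection of gp145 C.6980 at 2 dose levels". Protocol 5.2 (SAP 4.2) gives secondary objective 1: "To evaluate the safety and tolerability of 3 injections of gp145 C.6980 at 2 dose levels". The reactogenicity endpoint under each has the same wording, a frequency of severe local and systemic signs and symptoms, with no injection number and no time window.

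One analysis rule serves both objectives. Protocol 6.4.3.1 and SAP 10.3.1 say that, for each sign or symptom, a participant's "reactogenicity will be counted once under the maximum severity for all injection visits". Results are tabulated by severity and arm, and "Kruskal-Wallis tests will be used to test for differences in severity between arms". SAP 10.3.1 places the tests in the final analysis.

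The output lists add nothing by injection. SAP 11.1 has one reactogenicity table entry, maximum local and systemic summaries. SAP 11.3 has two reactogenicity figures, maximum local and maximum systemic. SAP 11.2 lists individual severe or life-threatening reactogenicities for the Safety Monitoring Board (SMB) reports.

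Other safety components are handled differently. Laboratory abnormalities are tabulated by arm at each postvaccination timepoint (Protocol 6.4.3.3, SAP 10.3.3). The SAE listing shows how many vaccinations the participant had received (Protocol 6.4.3.2, SAP 10.3.2).

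**The concern.** The trial separates one injection from three in its objectives, and it puts the one-injection question first. A statistician who follows the reactogenicity rule exactly will produce only the three-injection answer. The first endpoint listed under the primary objective would then be reported with a quantity that belongs to secondary objective 1.

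Two things are at stake. First, a reader of the final report could not tell how often a first dose of a product not previously tested in humans caused a severe reaction in each arm. Second, the between-arm test would compare maxima that may be driven by injections 2 and 3, which could mask or create a difference relative to injection 1. If the first-injection summary is chosen only after unblinded results are known, it is no longer prespecified.

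**Working it through.** **Does any planned output give a first-injection frequency by arm?** The plan states no per-injection rate, so there is no figure to reproduce. The check is of the text.

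| Planned item | Where | First-injection reactogenicity frequency by arm? |
|---|---|---|
| Tabulation by severity and arm | Protocol 6.4.3.1, SAP 10.3.1 | No: one count, maximum over all injection visits |
| Kruskal-Wallis tests | Same | No: the only defined severity is that maximum |
| Reactogenicity table and figures | SAP 11.1, 11.3 | No: titled as maxima, nothing by injection |
| Severe-reaction listing | SAP 11.2 | No: individual listing for SMB reports; injection number not mentioned |
| Safety review team (PSRT) review after vaccination 1 | Protocol 3 (Table 3-1 note), 4.3.2, 11.3 | No: first 9 participants, for an enrollment decision |

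Because each participant is counted once, the rule cannot be read as a separate count at each visit.

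**Could the result be produced?** Yes. Protocol 9.8 sets an assessment period of 7 full days after each vaccination. Protocol 6.4.3 notes that enrollment coincides with the first vaccination, so every enrolled participant contributes to an injection-1 table (planned denominators 25, 15 and 5). The all-injection maximum pools participants whatever number of injections they received.

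**How does the planned count relate to the injection-1 count?**

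- *Severe or worse.* A participant's maximum over all injections cannot be below the injection-1 grade. The planned count is therefore at least the injection-1 count: an upper bound.
- *A lower single-grade row.* Neither direction is assured. A participant who is mild at injection 1 and severe at injection 2 is mild in an injection-1 table but appears only in the severe row of the planned table. A participant with no reaction at injection 1 and a mild one at injection 2 does the reverse and adds to the planned mild row.

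**How far apart could the severe figures be?** Let p be the risk of a severe reaction at injection 1. The documents give no value, so p = 2%, 5% and 10% are assumptions. Assume also that the risk at injections 2 and 3 is no higher than p.

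- Lower limit: p.
- Upper limit, whatever the dependence within a participant: p1 + p2 + p3, at most 3p.
- Equal risks, independent, all three injections given: 1 - (1 - p)^3.

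| p | Lower limit | Independent | Upper limit |
|---|---|---|---|
| 2% | 2.0% | 1 - 0.98^3 = 5.9% | 6.0% |
| 5% | 5.0% | 1 - 0.95^3 = 14.3% | 15.0% |
| 10% | 10.0% | 1 - 0.90^3 = 27.1% | 30.0% |

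Expected participants with a severe reaction at p = 5%:

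| Arm | Injection 1 | Maximum over all injections (independent) |
|---|---|---|
| Group 2, n = 15 | 15 × 0.05 = 0.75 | 0.75 to 2.25 (2.14) |
| Group 1, n = 25 | 25 × 0.05 = 1.25 | 1.25 to 3.75 (3.57) |
| Both vaccine arms, n = 40 | 40 × 0.05 = 2.00 | 2.00 to 6.00 (5.71) |

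Discontinuation under Protocol 7.3.3 does not break these limits. A participant stopped for a related grade 4 reaction is already counted, and injections not given can only lower later risk.

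**The case against.** The strongest reply is that the reactogenicity endpoint in Protocol 5.1 carries no injection number, so the rule analyses the endpoint as worded. It is true that the mismatch begins between objective and endpoint. But the endpoint sits under an objective limited to one injection. If it is read as covering all injections, the primary objective and secondary objective 1 have the same reactogenicity result, and the distinction between them disappears.

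A second reply is that first-injection data are looked at elsewhere: the PSRT reviews two weeks of data after vaccination 1, and the SMB receives severe-reaction listings. Both are real safeguards, but the first covers 9 of 45 participants, and neither is specified as a frequency by arm.

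A third reply is that the consequence is small. Much of this stands. For severe reactions the error within an arm is conservative, the data are collected, and no sample size calculation or pause rule uses the pooled table. That limits the weight of the point but does not supply the missing result.

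Finally, the threefold ceiling rests on assumed risks. That stands too. If later injections are more reactogenic than the first, the ceiling fails and the gap can be wider. The lower limit p does not depend on that assumption.

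**Conclusion.** The point holds for reactogenicity. As written, the plan gives the primary objective no first-injection reactogenicity frequency by arm, and its all-injection maximum and test belong to secondary objective 1. On the assumptions shown, the planned severe-reaction figure could equal the injection-1 figure or be up to three times as large. The text finding needs no assumption; the size does. It should be corrected before the final safety analysis, and it is cheap to correct.

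Four stronger readings are tempting, and the documents do not support them:

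- *The rule hides first-dose harm.* Within an arm it cannot make severe reactions at injection 1 look rarer than they were.
- *Every planned frequency is an upper bound.* This is true only for a given grade or worse, not for each severity row.
- *The whole primary safety objective lacks a one-injection analysis.* Laboratory results are shown by timepoint, and individual SAEs can be placed by number of vaccinations received. For AEs, the rule that "a participant with multiple AEs within a category will be counted once under the maximum severity" states no onset window. That is a missing detail, not a stated rule to pool injections.
- *The SAE period is left open.* The phrase "Serious adverse events (SAEs) throughout the active surveillance period" is not defined and recurs under secondary objective 1, but Protocol 11.2.3 states an SAE reporting period, from enrollment to study completion or discontinuation. This needs clarification only.

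**What to change.** In SAP 10.3.1, 11.1 and 11.3, and in Protocol 6.4.3.1 when it is next revised:

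1. Add a descriptive table and a matching figure, by arm, of each participant's maximum reactogenicity severity on days 0-7 after injection 1. Name these as the primary-objective output.
2. Label the existing all-injection maximum, with its Kruskal-Wallis tests, as the output for secondary objective 1.

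A test on the injection-1 data is optional. If one is wanted, apply the planned Kruskal-Wallis test and report it as unadjusted, in line with Protocol 6.4 ("No formal multiple comparison adjustments will be employed for multiple safety endpoints"). That is up to 15 tests: the 14 measures listed in Protocol 5.1 plus the induration-or-erythema maximum. At an assumed 5% level, 15 × 0.05 = 0.75 would be expected to be significant by chance.

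As clarifications only, state the AE onset window for each objective and define the surveillance period named in the SAE endpoint, with reference to Protocol 11.2.3.

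The core change costs a SAP revision, one more table and one more figure. It needs no new data and no change to the sample size.

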#### 6.4.3.2 AEs and SAEs

AEs will be summarized using MedDRA System Organ Class and preferred terms. Tables will show by treatment arm the number and percentage of participants experiencing an AE within a System Organ Class or within preferred term category by severity or by relationship to study product. For the calculations in these tables, a participant with multiple AEs within a category will be counted once under the maximum severity or the strongest recorded causal relationship to study product. Formal statistical testing comparing arms is not planned since interpretation of differences must rely heavily upon clinical judgment.

A listing of SAEs reported to the DAIDS Regulatory Support Center (RSC) Safety Office will provide details of the events including severity, relationship to study product, time between onset and last vaccination, and number of vaccinations received.

#### 6.4.3.3 Local laboratory values

Box plots of local laboratory values will be generated for baseline values and for values measured during the course of the study by treatment arm and visit. Each box plot will show the first quartile, the median, and the third quartile. Outliers (values outside the box plot) will also be plotted. If appropriate, horizontal lines representing boundaries for abnormal values will be plotted.

For each local laboratory measure, summary statistics will be presented by treatment arm and timepoint, as well as changes from baseline for postenrollment values. In addition, the number (percentage) of participants with local laboratory values recorded as meeting Grade 1 AE criteria or above as specified in the Division of AIDS Table for Grading the Severity of Adult and Pediatric Adverse Events (section 9.8) will be tabulated by treatment arm for each postvaccination timepoint. Reportable clinical laboratory abnormalities without an associated clinical diagnosis will also be included in the tabulation of AEs described above.

#### 6.4.3.4 Reasons for vaccination discontinuation and early study termination

The number and percentage of participants who discontinue vaccination and who terminate the study early will be tabulated by reason and treatment arm.

### 6.4.4 Immunogenicity analysis

#### 6.4.4.1 General approach

For the statistical analysis of immunogenicity endpoints, data from enrolled participants will be used according to the initial randomization assignment regardless of how many injections they received. Additional analyses may be performed, limited to participants who received all scheduled injections per protocol. Assay results that are unreliable, from specimens collected outside of the visit window, or from HIV-infected participants postinfection are excluded. Since the exact date of HIV infection is unknown, any assay data from blood draws 4 weeks prior to an infected participant's last seronegative sample and thereafter may be excluded. If an HIV-infected participant does not have a seronegative sample postenrollment, then all data from that participant may be excluded from the analysis.

Discrete categorical assay endpoints (eg, response rates) will be analyzed by tabulating the frequency of positive response for each assay by antigen and treatment arm at each timepoint for which an assessment is performed. Crude response rates will be presented with their corresponding 95% confidence interval estimates calculated using the score test method [36]. Because of the small numbers of control participants, no adjustment will be made to the vaccine arm estimates for the false positive rates in the control arms. Barnard or Fisher's exact tests, as specified in the SAP, will be used to compare the response rates of the 2 vaccine arms, with a significant difference declared if the 2-sided p-value is  $\leq 0.05$ . In general Barnard's is preferred since under most circumstances it is more powerful than Fisher's [37].

For quantitative assay data (eg, IgG binding Ab response from the multiplex assay or CD4+/CD8+ T cell response from the ICS assay), graphical and tabular summaries of the distributions by antigen, treatment arm, and timepoint will be made. For all primary and secondary immunogenicity endpoints, box plots and plots of estimated reverse cumulative distribution curves will be used for graphical display of all of the study arms. Typically the results will be shown for each vaccine arm and for the control arm separately.

The difference between arms at a specific timepoint may be tested with a nonparametric Wilcoxon rank sum test if the data are not normally distributed and with a 2-sample t-test if the data appear to be normally distributed. An appropriate data transformation (eg,  $\log_{10}$  transformation) may be applied to better satisfy assumptions of symmetry and homoscedasticity (constant variance).

